**HIV service delivery outcomes** (other/exploratory outcome). Providers will be asked to estimate to the best of their ability the approximate *percentage of patients or clients lost to care over the past 6 months*, *percentage of patients who were virologically suppressed over the past 6 months*, and *percentage of PrEP initiation over the past 6 months*. The participants will be asked to provide an estimate between 0 to 100% and will be given the option for N/A and Don't Know. Because this is a pilot RCT conducted online/remotely with providers, collecting direct patient-level outcomes will not be feasible and there are no existing provider-reported measures for these outcomes; however, we were encouraged by the funding agency to include HIV-related outcomes. If the results from the current study are promising, we plan to include patient/client-level outcomes in future research (e.g., patient/client experience, trust toward provider and healthcare organization, patient/client adherence to treatment recommendations and medication, and care engagement).

**Process evaluation outcomes (intervention participants only).** Participants who are randomized to receive the provider training will be asked in the survey at post-training to rate the *acceptability*, *appropriateness*, and *feasibility* of the provider intervention. These items are adapted from the Acceptability of Intervention Measure, Intervention Appropriateness Measure, and Feasibility of Intervention Measure. We will ask participants to rate the format and content of the provider intervention separately. Participants will also complete a qualitative interview at post to provide feedback on the acceptability of the intervention. The interview will cover four acceptability constructs, including attitude (e.g., overall satisfaction), opportunity costs (e.g., barriers to participation), perceived effectiveness, and self-efficacy (e.g., participant's confidence that they can perform the skills learned in the intervention). We have piloted the interview protocol during the usability test.

**Potential covariates.** We will assess the provider's socio-demographic characteristics (e.g., age, race and ethnicity, sexual orientation and gender identity) and clinical practice characteristics (e.g., years of experience) as a provider working with patients at risk or living with HIV.

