## Statistical Analytic Plan

Consistent with R34 guidelines, our primary purpose is to collect preliminary data and exploratory analyses on feasibility, acceptability, and outcomes, to calculate effect size estimates to assist planning for a fully powered RCT. Hence, we do not expect to have sufficient statistical power to adequately examine effects, and conducting formal tests for measures of effect size is not justified with limited sample size. Multilevel modeling will be used to account for multiple observations nested within providers. The intervention effect of interest will be a significant interaction between intervention condition (intervention vs. control) by time (pre, post, 6-month follow-up) on outcome variables. We hypothesize that participants in the intervention condition, compared to those in the control condition, will show greater increases in the number of empathic responses to medical mistrust, perceived importance, and the number of strategies (e.g., validation, MI-consistent statements, behavioral change techniques) used during simulated role-play, and perceived importance from pre to post and 6-month follow-up; intervention participants will also show a greater reduction in the percentage of patients lost to care, a greater increase in the percentage of patients virologically suppressed, and a greater increase in the percentage of patients who initiated PrEP, relative to control participants, from pre to post and 6-month follow-up. Analyses will use the standard intent-to-treat approach, in which we will analyze participants as belonging to the intervention condition they were randomized to, regardless of later non-response or loss at follow-up. The multilevel modeling approach uses a full information maximum likelihood estimator, meaning that all information is included in the analysis under the assumption that the data are missing at random or missing completely at random. For the quantitative process evaluation measures (i.e., AIM, IAM, FIM), we will report the descriptive statistics (e.g., mean, standard deviation, and range).

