## Protocol Amendment

The study protocol was last reviewed by the study Data Safety and Monitoring Board (DSMB) in April 2023, prior to recruiting the first participant. Since then, there have been several changes to the protocol. Initially, we planned to conduct post-assessments approximately 4-6 weeks following the baseline for control participants. However, scheduling training participants proved to be time-consuming (particularly during the summer), resulting in the interval between the baseline and immediate post-assessment extending to approximately 2-3 months. Consequently, control participants were also assessed 2-3 months following their baseline assessment. Secondly, the study team decided to eliminate the collection of role-play assessments at 6 months due to several considerations: 1) the primary interest and timeframe for the primary outcomes are changes from pre to post, 2) the response rate for role-play was low at post-assessment (see Table 2), 3) the participant burden was high compared to surveys, 4) conducting role-play assessments was time-consuming for the study team, necessitating a reallocation of resources to focus on pre-to-post changes, and 5) the surveys collected from baseline to 6-month follow-up include open questions on helpful responses to mistrust in hypothetical patient scenarios, which serve as proxies for provider responses in role play simulations. Thirdly, we increased the incentives for completing the survey and the brief role-play assessment at post-assessment or follow-up. Previously, we offered \$50 for completing both the survey and the assessment with a study coordinator or research assistant. However, participants in the control group received no training and had limited contact with the study team after the baseline assessment was completed (in contrast, the training group received numerous scheduling calls and completed training, including a 2-hour live session). We observed a relatively low response rate for the post-assessment in the control group. Therefore, we increased the incentives to \$50 for completing the survey and an additional \$50 for the assessment. This amendment was approved by RAND's Human Subject Protection Committee (RAND's IRB) in November 2023.

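### The analysis plan rules out formal testing, yet defines the intervention effect as a significant three-visit interaction and does not single out the pre-to-post contrast that the amendment calls primary

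*Combined protocol and SAP*

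**What the plan says.** The Statistical Analytic Plan opens with the purpose usual for a pilot: preliminary data, and effect size estimates to help plan a fully powered trial. It concedes that "we do not expect to have sufficient statistical power to adequately examine effects" and adds that "conducting formal tests for measures of effect size is not justified with limited sample size".

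After one sentence on multilevel modelling it continues: "The intervention effect of interest will be a significant interaction between intervention condition (intervention vs. control) by time". Time is listed as pre, post and 6-month follow-up, and the definition covers the outcome variables without distinction. No alpha or sidedness is given, and the plan does not say whether the interaction is a joint test or a single contrast. The hypotheses treat the two intervals together, for example strategies "used during simulated role-play, and perceived importance from pre to post and 6-month follow-up", and rank neither first.

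The Protocol Amendment section says that "the study team decided to eliminate the collection of role-play assessments at 6 months". One reason given is that "the primary interest and timeframe for the primary outcomes are changes from pre to post"; another is that "the response rate for role-play was low at post-assessment". Under Assessment Procedures, the two outcomes labelled primary are the adapted HRQ and the role-play simulation.

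**The concern.** There are two linked problems.

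- **Estimation against testing.** The plan's purpose is an estimate, but the sentence defining the intervention effect makes significance part of the definition. Saying that only tests of effect size measures are excluded does not remove the conflict, because the interaction is the intervention effect.
- **Which contrast.** The amendment gives pre to post as the primary timeframe for the primary outcomes. The analysis section still points to an interaction over three visits. For the HRQ, which keeps all three visits, that interaction can be driven by what happens at 6 months.

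A reader following the analysis section literally could report an intervention effect on a primary outcome when the arms did not differ over the primary timeframe. The number carried into planning the full trial could then answer a different question from the one the team says it is asking.

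**Working it through.** The plan gives no power, alpha, SD or effect size, so there is no figure of its own to reproduce. The check asks how often each reading of the HRQ interaction would be significant.

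**From the documents.** 30 providers per arm (Abstract, Aim 2); three HRQ visits; pre to post as the primary timeframe (Protocol Amendment).

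**Assumed, because the documents are silent.** Two-sided 5%; complete data; equal variance at each visit and equal correlation between visits; approximately normal outcomes; true between-arm difference of 0 at post and 0.5 at 6 months, in units of the change-score SD.

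**Step 1: covariance of the two contrasts.** Let D1 be the between-arm difference in pre-to-post change and D2 that in pre-to-6-month change. Both use the same baseline, so with change-score variance 1 the two changes have covariance 0.5. Then

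V = (2/30) × [[1, 0.5], [0.5, 1]].

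**Step 2: joint 2-df test.** The noncentrality is λ = d′V⁻¹d with d = (0, 0.5). The inverse of [[1, 0.5], [0.5, 1]] has diagonal 1/0.75, so

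λ = 15 × 0.25/0.75 = 5.0.

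Referred to F(2, 116), the chance of p < 0.05 is 49%.

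**Step 3: pre-to-post contrast.** The true value of D1 is 0, so the chance of p < 0.05 is 5%.

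**Step 4: the reverse pattern.** With d = (0.5, 0), λ is again 5.0 and the joint test is significant 49% of the time. The pre-to-post contrast has standard error √(2/30) = 0.258 and noncentrality 0.5/0.258 = 1.94, which gives 48% on 58 df.

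| True difference (change-score SD) | Joint 2-df test | Pre-to-post contrast |
|---|---|---|
| 0 at post, 0.5 at 6 months | 49% | 5% |
| 0.5 at post, 0 at 6 months | 49% | 48% |

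The joint test cannot tell these two patterns apart; the pre-to-post contrast can.

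**Step 5: sensitivity to units.** In change-score SD units the result does not depend on the within-provider correlation. If 0.5 is instead in baseline SD units, the joint test (chi-square approximation) is significant 38%, 50% and 74% of the time for a 6-month-only difference at correlations 0.3, 0.5 and 0.7. The pre-to-post contrast stays at 5%.

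**Step 6: what estimation would give.** At 30 per arm the 95% CI half-width for the pre-to-post contrast is 2.00 × 0.258 = 0.52 change-score SD. In baseline SD units (normal approximation) it is about 0.60, 0.51 and 0.39 at correlations 0.3, 0.5 and 0.7. Dropout would widen these.

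**Role-play.** With only pre and post collected, the interaction has one degree of freedom and is the pre-to-post contrast. The three-visit definition cannot apply to it.

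**The case against.** The best reply is that this is an openly exploratory pilot with loose wording, and that the combined document already supplies the missing pieces. Much of that is right, and it limits what can be inferred.

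- **That the plan ignores pre-to-post change.** It does not. The hypotheses state between-arm differences in change from pre to post, jointly with 6 months. What is missing is the ranking that the amendment gives.
- **That significance decides what is reported or whether the programme goes on.** The documents do not say so. Effect size estimation is a stated aim, and nothing says estimates will be withheld when p > 0.05. The Assessment Procedures sentence "If the results from the current study are promising, we plan to include patient/client-level outcomes in future research" leaves its criterion undefined but does not tie it to a p-value.
- **That the interaction might be a linear trend.** Time is listed as named visits and the hypotheses are changes from pre, so this reading has little support. The point does not need it.
- **That the role-play analysis is left ambiguous.** With two visits it reduces to the right contrast; only the wording is out of date.
- **That the sample is too small, or that multiplicity is uncontrolled.** The plan already concedes low power, and error-rate concerns over several primary counts fall away once significance is not the criterion.

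It is also fair that the two readings of the HRQ interaction barely differ for a post-only effect (49% against 48%). They separate sharply in the 6-month-only pattern, which is an extreme case.

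Two things remain: the internal conflict over testing, and an effect definition not aligned with the primary timeframe. The amendment sentence states a current timeframe as the reason for a current decision, so it cannot be set aside as superseded text.

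**Conclusion.** The point holds as a fault of specification, and it should be fixed. The analysis section calls formal testing unjustified and then defines the intervention effect by significance, without an alpha. It also does not single out the contrast that the same document calls primary. Both findings rest on the text alone and need no assumptions.

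The size is illustrative. For the HRQ at 30 per arm, a 6-month-only difference of 0.5 change-score SD would meet a joint reading of the definition about 49% of the time, against 5% for the primary contrast. That rests on the assumed alpha, effect pattern, complete data and normal approximation; the planned outcomes are counts. It shows that the choice can matter, not that this pattern is likely. Nothing here shows that the sample size is wrong or that results will be suppressed.

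**What to change.** In the Statistical Analytic Plan, delete the word significant and redefine the effect along these lines:

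- **Primary outcomes (HRQ and role-play).** The intervention effect is the between-arm difference in pre-to-post change from the multilevel model with time as a categorical factor. It is reported as an estimate, a standardised effect size and a 95% CI, whatever its p-value.
- **6-month contrast.** Secondary for the HRQ; not estimated for role-play.
- **Exploratory outcomes.** Report pre-to-post and pre-to-6-month estimates with 95% CIs, without ranking pre to post as primary. The amendment limits that timeframe to the primary outcomes. The service-delivery items also ask about the past 6 months, while post came about 2-3 months after baseline, so 3 to 4 of the 6 recalled months precede baseline.
- **P-values.** Any that are shown are descriptive only.

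Record the date of the change relative to any between-arm look at outcomes. This matters because the Interim Data Monitoring section plans interim analyses as participants finish, and post-assessments had begun by the November 2023 document.

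**Cost.** No new data are needed, and no new model: with time categorical, the pre-to-post contrast is already a coefficient. The team gives up defining a pilot effect by significance and has to disclose a mid-trial change to the analysis.

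### The condition-by-time effect, as conventionally fitted, is a difference in change that ignores the equal baseline means given by randomisation, and so generally loses precision

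*Combined protocol and SAP*

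**What the plan says.** The Statistical Analytic Plan states that "Multilevel modeling will be used to account for multiple observations nested within providers" and defines the effect of interest as "a significant interaction between intervention condition (intervention vs. control) by time (pre, post, 6-month follow-up) on outcome variables". Its hypotheses are worded as differences in change: "participants in the intervention condition, compared to those in the control condition, will show greater increases in the number of empathic responses to medical mistrust". Estimation is by full information maximum likelihood. The stated purpose includes using the data "to calculate effect size estimates to assist planning for a fully powered RCT"; the section expects insufficient power and regards formal tests of effect size as unjustified.

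The Protocol Amendment section says that "the primary interest and timeframe for the primary outcomes are changes from pre to post". It also reports that "the response rate for role-play was low at post-assessment" and, separately, "We observed a relatively low response rate for the post-assessment in the control group".

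The potential covariates under Assessment Procedures are the provider's "socio-demographic characteristics (e.g., age, race and ethnicity, sexual orientation and gender identity) and clinical practice characteristics (e.g., years of experience"). The baseline value of the outcome is not among them, and the Statistical Analytic Plan names no covariate in the model. Nothing says whether a baseline difference between arms is to be estimated.

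**The concern.** In a randomised comparison the two arms have the same expected baseline mean. A model with condition, time and their product does not use this. It estimates a separate baseline mean in each arm, and its post interaction subtracts the whole observed baseline difference, whatever the pre-post correlation. Full information maximum likelihood deals with missing outcomes; it does not make the arms equal at baseline.

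The consequence is a wider interval, not bias. The trial plans only 60 providers, the post assessment has already suffered non-response, and a main product is an effect size with which to plan a larger trial. Precision given up at the modelling stage is then hard to replace, while the baseline data needed to recover it are already being collected.

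**Working it through.** **Inputs from the documents.** 60 providers, 30 per arm (Aim 2); baseline as a level of time; pre-to-post as the contrast of primary interest. The documents state no SD, correlation, response rate, power or target effect, so there is no figure of the plan's own to reproduce.

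**Assumed inputs.** Baseline SD 1; k = post SD / baseline SD; pre-post correlation rho of 0.3, 0.5 or 0.7; linear model, same covariance in both arms. Two response patterns: complete data, and an illustrative 25 trained and 20 control providers observed at post. Providers with baseline only are kept in both models.

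**Formulas.** Let n1, n0 be the numbers at baseline and m1, m0 the numbers observed at post.

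- Common baseline mean: Var = k²(1 − rho²)(1/m1 + 1/m0)
- Planned model, conventional form: Var = k²(1 − rho²)(1/m1 + 1/m0) + (1 − rho·k)²(1/n1 + 1/n0)

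The second term is the price of estimating a baseline difference. It is never negative and is zero only if rho·k = 1. With complete data and k = 1 the variance ratio reduces to 2/(1 + rho).

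**Worked case, rho = 0.5, k = 1.**

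- Complete data: common baseline 0.75 × 2/30 = 0.0500; planned 0.0500 + 0.25 × 2/30 = 0.0667. SE ratio √(0.0667/0.0500) = 1.15. 95% CI half-width 1.96 × √0.0667 = 0.51 against 1.96 × √0.0500 = 0.44 baseline SD. The variance ratio of 1.33 means that 60 providers analysed as planned give the precision of 60/1.33 = 45 under the alternative.
- 25/20 observed: common baseline 0.75 × (1/25 + 1/20) = 0.0675; planned 0.0675 + 0.0167 = 0.0842. Half-widths 0.57 and 0.51. The absolute excess is the same 0.0167; only the relative loss shrinks.

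**Excess SE of the planned estimate (rho 0.3 / 0.5 / 0.7).**

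| k | Complete data, 30 + 30 | 25 + 20 observed at post |
|---|---|---|
| 1 | 24% / 15% / 8% | 18% / 12% / 6% |
| 1.25 | 13% / 6% / 1% | 10% / 4% / 1% |
| 1.5 | 7% / 2% / 0% | 5% / 1% / 0% |

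If the spread shrank (k = 0.75), the complete-data figures would be 47% / 39% / 34%, but nothing in the documents suggests this.

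**Checks.** In simulated three-visit complete data with a random intercept, the fitted condition-by-post interaction equalled the between-arm difference in mean change to rounding error in every data set. Because the primary outcomes are counts, a second check used skewed counts (gamma-Poisson, 20,000 trials per setting, 30 per arm, baseline mean 6, control mean unchanged, linear model on the count). The SE excess was:

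- no training effect: 21% (rho 0.35) and 11% (rho 0.59);
- trained mean rising to 9: 12% (rho 0.37, k 1.19) and 2.5% (rho 0.61, k 1.22);
- trained mean doubling to 12: about 0% (rho 0.62, k 1.46).

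**The case against.** The strongest reply has four parts.

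**The fault is inferred.** The plan never says that a baseline condition effect will be estimated, and its wording is compatible with a common-baseline model, whose effect terms are themselves condition-by-visit interactions. This stands, and it is why the point is limited to the conventional fit. But a plan that leaves this open will most likely be fitted in the default way, and saying which model is meant costs a sentence.

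**Both estimators are valid, and this is an exploratory pilot.** True: there is no bias and no power error. Feasibility and acceptability are also aims, and an interval of about half an SD either side is wide under either model. The plan nonetheless gives effect size estimation as a purpose, and precision is the criterion for that.

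**The gain is smallest where the hypothesis points.** If training raises the counts, their spread will probably rise too, so k above 1 is a likely case. At k = 1.25 and rho 0.5 the half-width falls only from 0.58 to 0.55, or from 0.66 to 0.64 with 25/20 observed. This stands as a limit on size. Under the linear equal-covariance model the common-baseline estimate is never less precise. With a log link the formula does not carry over directly.

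**A common baseline mean requires that baseline precede any effect of allocation.** The order of randomisation and baseline assessment is not stated outright. However, the Informed Consent section has participants consent before baseline to possible selection for training, and the Intervention Description has the Module 1 recording sent only after baseline. The documents support the condition, but the plan could confirm it.

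**Conclusion.** The concern holds as a matter of precision only. The stated interaction, fitted conventionally, is a difference in change, and no section sets a common baseline mean or adjusts for the baseline outcome. The loss in SE ranges from roughly a quarter (rho 0.3, equal SDs, complete data) to nothing (rho·k near 1). It depends on a correlation, an SD ratio and response numbers that the documents do not give, and on a linear model for the counts. The change should be made because it is nearly free and serves a stated purpose of the analysis; it does not correct an invalid analysis.

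**What to change.** In the Statistical Analytic Plan, keep the full information maximum likelihood multilevel model and specify:

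- categorical time, with condition-by-post and condition-by-6-month terms and no condition effect at baseline;
- variances allowed to differ by visit, since forcing one variance would weight the baseline by something other than its regression slope;
- the condition-by-post term with its 95% confidence interval as the primary effect estimate, in line with the pre-to-post focus in the Protocol Amendment section;
- for role-play, which is no longer collected at 6 months, the condition-by-post term only.

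Complete-case ANCOVA on the baseline value can serve as a sensitivity analysis. It should not replace the model, because it drops providers who have only baseline data.

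The cost is one or two sentences, with no extra data, staff or participants. Visit-specific variances add one or two parameters, so name a fallback in case the model does not converge. The same text should state the distribution and link for the counts, because the size of the gain shown here applies to a linear model.

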## **Intervention Description**

Participants who are randomized to receive the provider training will complete three modules. The provider training protocol described below was tested in the pilot usability test with 18 providers and they were generally satisfactory in terms of the content and format of the training. Minor revisions to the training material will be made to improve the process (e.g., allocating more time for the role plays in the breakout room, minor edits of selected slides) prior to the beginning of provider training groups for the pilot RCT. Module 1 will be a recorded presentation (45 min) covering background information; the participants can view on their own time prior to the live session or attend an optional live session to view the module 1 material. Module 2 will be a 2-hour live training session focusing on skill building. Module 3 will be a workbook focusing on review, reflection, and making an action plan; the participant will complete and submit within one week of completing the live session (up to 30 min) or attend an optional 30-min live-session that will be facilitated by the trainers to complete this.

We will record the attendance of the optional sessions for module 1 and 3 and elicit participant's feedback on their feasibility and usefulness, which will help planning for future studies of this intervention.

The total time for completing the training is approximately 3.5 hours. Intervention participants will receive an additional \$200 for completing the training and the qualitative feedback interview at post-training. The provider training will occur online, and the participants will receive intervention material via email and participate in a 2-hour live training session via Zoom. They will submit workbook (module 3) via email to the study coordinator. The training will be delivered by three experienced provider trainers from CAPTC. The lead trainer is identified as a Black gay man, and all trainers will include their self-identification in the self-introduction at the beginning of module 1 and 2. All trainers have over 20 years of experience with provider training on a range of topics covering HIV/STD, stigma, and motivational interviewing. The feedback from the pilot usability test was positive on the trainers.

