A brief description of the three modules is presented in the Appendix. Module 1 (background) aims to increase knowledge about intersectional stigma, discrimination, and medical mistrust, and how these experiences impact adherence, care engagement, and health outcomes in people living with HIV. Module 1 also includes HIV care consumers' recommendations and quotes about what they think providers could do to build trust and respond to mistrust, based on our interviews with HIV care consumers during the formative stage of this study. The background section will serve as a crucial foundation for module 2 skill building. There will also be a workbook that the participants will use to write down responses to discussion questions while viewing the recording; the participants will be asked to return the workbook to the study coordinator via email. The recording link will be sent to the participants via email following the completion of baseline assessment and a reminder to complete module 1 will be sent one week prior to the module 2 live training session. We will also schedule an optional live session the participants can join to view module 1.

Module 2 (skill building) includes a section on validation skills and a section on basic motivational interviewing skills, such as asking for permission before sharing, offering information in elicit-offer-elicit format, using open questions, and responding in a non-judgmental and non-confrontational style. The skill building will include didactic presentations about the skills (e.g., definitions, examples) and interactive exercises to practice the skills via role-play exercises in pairs in breakout rooms and group discussions.

Module 3 (review/reflection and planning ahead) is a workbook that the participant will be asked to complete on their own and submit to the study coordinator within 1-2 weeks of completing the training. The workbook includes 1) a review of key skills learned during the training, 2) written exercises on how to respond to hypothetical patient scenarios, and 3) written responses to open questions about goal setting and action plans to uptake the skills learned in this training. We will also offer an optional live session facilitated by the trainers for those who would like to complete this workbook with the opportunity for questions and discussion.

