## **Assessment Procedures**

All participants will be asked to complete the assessment protocol at baseline, immediately post-training (or approximately 4-6 weeks following baseline for control group participants), and 6-month follow-up. There are three types of assessment: 1) online survey (about 30 min), 2) role-play simulation (about 30 min), and 3) qualitative feedback interview (about 45 min) for process evaluation. The role-play simulation and qualitative feedback interview data collection will be led by an experienced project coordinator at RAND, who identifies as a Latina cisgender woman, is experienced with supporting HIV and stigma research, and is trained in motivational interviewing (e.g., is a certified MITI coder). Participants will receive \$50 for completing each of the three assessments at baseline, post-training, and 6-month follow-up (\$150 total).

The online survey includes sociodemographic characteristics (e.g., race, ethnicity, age) and clinical practice characteristics (e.g., position, years in practice), provider training outcomes (e.g., written responses to short

patient scenarios), self-reported HIV service delivery outcomes (e.g., percentage of patients/clients lost to follow-up), and process evaluation outcomes (e.g., ratings of the intervention acceptability). Below we describe each measure in detail.

**Provider Training Outcomes:** *Provider's helpful/empathetic responses toward medical mistrust* (primary outcome) will be assessed using the paper-and-pencil Helpful Response Questionnaire, adapted specifically for this study following other adaptation examples in prior research. The adapted HRQ includes six hypothetical patient scenarios presenting mistrust-related statements that patients experiencing intersectional stigma and discrimination may express. During the adaptation, we tried to patient's demographic characteristics (e.g., gender, age, sexual orientation, racial/ethnic groups) in the hypothetical scenarios. Helpful/empathetic responses will be operationalized as the number of MI-consistent statements and validation used in the written responses, following prior studies. The number of reflections/validation and MI-consistent statements will be coded using the Motivational Interviewing Skills Coding.

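### Three exploratory service-delivery outcomes look back six months but are hypothesised to differ at the immediate post-training survey; name the 6-month contrast as their effect estimate

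*Combined protocol and SAP*

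**What the plan says.** The service-delivery paragraph of Assessment Procedures labels three provider-estimated percentages as exploratory. Each has a six-month recall period: "percentage of patients or clients lost to care over the past 6 months", viral suppression, and PrEP initiation.

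Assessment Procedures places these items in the online survey, which is given at baseline, "immediately post-training (or approximately 4-6 weeks following baseline for control group participants), and 6-month follow-up". Protocol Amendment later lengthens the baseline-to-post interval to about 2-3 months in both arms and still calls the second assessment immediate. Nothing shortens the recall period for that survey.

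The Statistical Analytic Plan hypothesises arm differences on all three items at both follow-up times, ending with "a greater increase in the percentage of patients who initiated PrEP, relative to control participants, from pre to post and 6-month follow-up". It defines the effect generically: "The intervention effect of interest will be a significant interaction between intervention condition (intervention vs. control) by time (pre, post, 6-month follow-up". It does not say whether time is categorical, or whether the post and 6-month contrasts are read separately. It also states that "conducting formal tests for measures of effect size is not justified with limited sample size" and gives the aim as effect sizes for planning a full trial.

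Protocol Amendment gives pre to post as the timeframe of interest for the primary outcomes. No section says whether the 6-month survey is counted from baseline or from the post assessment.

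**The concern.** A percentage recalled over six months can respond to training only through the part of the window that comes after training. At a survey given straight after the live session, that part is close to nil. Part of the post window is also the same calendar time that the provider already reported on at baseline.

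The pilot is meant to supply effect sizes. A near-zero pre-to-post estimate on these items could be read as no service-delivery benefit, when the measurement could hardly have shown one. A non-zero estimate would mostly reflect noise, or reporting by providers who know which arm they are in. The protocol says "If the results from the current study are promising, we plan to include patient/client-level outcomes in future research", so a misread contrast could feed into that judgement.

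If the post and 6-month contrasts were pooled or tested jointly, the uninformative one would also dilute the informative one.

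**Working it through.** The plan gives no figure to reproduce here. The check is arithmetic on windows of time.

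**Inputs**
- Look-back: 6 months = 26.1 weeks (Assessment Procedures).
- Baseline-to-post interval T: 2-3 months, or 8.7-13.0 weeks (Protocol Amendment).
- Lag L from live session to post survey: not stated beyond immediate. Intervention Description has two workbook timings, "the participant will complete and submit within one week of completing the live session" and "submit to the study coordinator within 1-2 weeks of completing the training". I use 1 and 2 weeks as a plausible lag if the survey is done by the workbook deadline. Lags of 4-6 weeks are an assumption, added only to show the range.

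**1. Share of the post look-back after the live session = L / 26.1**

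| Lag (weeks) | Share |
|---|---|
| 0 | 0% |
| 1 | 1/26.1 = 3.8% |
| 2 | 2/26.1 = 7.7% |
| 4 (assumed) | 4/26.1 = 15.3% |
| 6 (assumed) | 6/26.1 = 23.0% |

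**2. Most generous reading.** The module 1 recording is sent after baseline, so count all time since baseline as exposed. Share = T/6: 2/6 = 33% and 3/6 = 50%.

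**3. Overlap of the post window with the baseline window** = (6 − T)/6: 4/6 = 67% and 3/6 = 50%.

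**4. Share of the 6-month look-back after the live session**
- Counted from the post assessment: 100%.
- Counted from baseline: (26.1 − (T − L))/26.1.
  - No lag: 67% (T = 2 months) and 50% (T = 3 months).
  - 2-week lag: (26.1 − 6.7)/26.1 = 74% and (26.1 − 11.05)/26.1 = 58%.

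**5. If the two follow-up contrasts were averaged equally,** the mean exposed share would be:

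| Lag | 6-month survey counted from post | Counted from baseline |
|---|---|---|
| 0 | (0 + 100)/2 = 50% | (0 + 50)/2 = 25% to (0 + 67)/2 = 33% |
| 2 weeks | (7.7 + 100)/2 = 54% | (7.7 + 57.7)/2 = 33% to (7.7 + 74.3)/2 = 41% |

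**Illustration, on assumed values.** Suppose a fully exposed window would show a difference of 0.5 SD, and the effect is immediate and proportional to exposed time. The post contrast would then be 0 to 0.5 × 0.077 = 0.04 SD. The 95% half-width with 30 per arm is 1.96 × √(2/30) = 0.51 SD.

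Steps 1-5 are shares of time, not predicted effects.

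**The case against.** **The harm to the estimate is conditional.** With time as a categorical factor, the model already yields a separate 6-month contrast, and the plan nowhere proposes averaging. This stands. Dilution arises only under pooling or a joint test, and step 5 describes that case alone. The plan leaves the choice open, and the pre-to-post hypothesis on these items is explicit either way.

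**Removing a hypothesised contrast mid-trial could look like outcome switching.** Post assessments were already under way when the amendment was written, and Interim Data Monitoring foresees analyses as participants finish. The worry is fair but small. The outcomes are exploratory, the reason is the timing in the design rather than any result, and the post values would still be reported.

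**The 6-month contrast may share the defect.** If it is counted from baseline, 33-50% of its window precedes the live session at no lag. This is why the anchor must be stated. Even so, a window that is 50-67% exposed is far more informative than one at 0-8%.

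**Reporting by providers who know their arm affects the 6-month survey too.** This stands, and the change does not cure it.

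**Viral suppression may be answered as a current status.** This also stands. The item does not say whether it is a status or an event, so its window share may not translate into dilution.

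**The lags are not documented.** Only the zero-lag figure and the since-baseline bound rest directly on stated timings. The conclusion does not need the others.

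**Conclusion.** The concern holds, as a minor point. For these three outcomes, the post survey asks about a period of which 0-8% follows the live session if the survey comes within two weeks, 15-23% on an assumed lag of 4-6 weeks, and at most 33-50% on the reading that counts everything since baseline. The pre-to-post contrast on them should not be offered as an effect of completed training. The finding is most secure for loss to care and PrEP initiation, and less certain for viral suppression.

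It does not touch the primary skill outcomes, which have no recall window and for which a pre-to-post comparison is natural. The stakes are further limited by the exploratory label, the disclaimer of formal tests, and the intention to use patient-level outcomes in later research.

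**What to change.** In the Statistical Analytic Plan:

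- Remove the pre-to-post hypothesis for loss to care, viral suppression and PrEP initiation.
- Name the baseline-adjusted arm difference at 6 months, from the multilevel model with categorical time, as the effect estimate for each.
- Keep the post values in the likelihood model and report them descriptively, not as a service-delivery effect.
- State the anchor actually used for the 6-month survey. If it is baseline, report the share of each window that follows training.
- Date the change and record that it rests on the timing of the look-back, not on observed data.

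The survey schedule should not be altered mid-trial, because the same survey carries the Helpful Response Questionnaire, a primary outcome.

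The cost is a few sentences of wording and one fewer exploratory contrast. No survey item, survey date or collected value changes.
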